## 2. Overall objectives

The primary objective of the study is to evaluate the impact of sending behavioral nudges to clinicians, as compared to usual practice, on completion of palliative care referrals among patients with advanced cancer. Our secondary objectives are to identify the impact of prompted palliative care referrals on quality of life, acute care utilization, and end-of-life utilization.

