### *3.2 Secondary outcomes*

- Change in quality of life between 0 and 9 weeks (as measured by the Functional Assessment of Cancer Therapy – General (FACT-G) among patients who receive palliative care compared to matched controls) (**Appendix A**)
- Quality of life at 9 weeks (as measured by the Functional Assessment of Cancer Therapy – General (FACT-G) among patients who receive palliative care compared to matched controls)

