For patients whose clinician pods are randomized to the intervention arm, the care team pod will receive an EPIC in-basket message indicating that the patient is eligible for Palliative Care and that a default referral order has been pended for that patient. Clinicians will be given an opportunity to respond if they do not want their patient to be referred to palliative care. For clinicians who do not respond, after the allotted time, the Clinical Research Coordinator will reach out to the patient to introduce palliative care and ask if ABBCI staff can schedule an appointment. For non-English speaking patients, an interpreter will assist research staff. For clinicians who respond no, the pended order will be removed and no patient contact by the research team will occur.

For eligible patients whose clinician pods have been randomized to the control arm, no intervention will be provided. Clinicians will refer patients to palliative care based on their usual practice.

Among patients in the intervention arm for whom palliative care referral is placed, who accept for a scheduler to call them to make an appointment, a trained research coordinator will approach 40

patients as a convenience sample to administer a baseline FACT-G survey (**Appendix A**). 40 randomly selected patients, matched on categories including age category and type of cancer, will be selected from the pods not receiving the intervention. For patients that choose to enroll in the survey component, a baseline FACT-G survey will be administered prior to discharge in-person via paper or electronically. Surveys will be repeated at 3, 6, 9, and 18-week intervals by either telephone or in-person at an in-person visit. For patients that complete the 9-week survey or any survey prior, a \$50 gift card will be given at the 9-week time point. Patients who miss their visits with palliative care will be contacted by the coordinator to identify why (**Appendix F**) and reschedule the appointment.

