## 9. Analysis plan

We will use REDcap, a HIPAA-compliant and secure database tool, to track all components of the study. Descriptive statistics will be used to estimate the frequencies, means, and standard deviations of the study variables. Differences between study groups in baseline characteristics and clinical outcomes will be assessed with the use of two-sided Fisher's exact tests and chi-square tests for categorical variables and independent-samples Student's t-tests for continuous variables. The unit of analysis will be the patient.

The primary study endpoint is a binary patient-level variable indicating completion of a palliative care visit within 24 weeks of the clinician behavioral nudge. This analysis will be conducted as a time-to-event analysis among all eligible advanced cancer patients. Cox proportional hazard regression analyses, adjusted for baseline covariates, will be used to examine the effect of nudges on completion of palliative care consultation for advanced cancer patients. Competing risk caused by patients who die within 24 weeks will be considered as censored in the analysis. Covariates will include patient and cancer-related variables. Patients will be followed for 24 weeks or until death. Using a longitudinal multilevel mixed-effects model with clustering by discharging clinician (intraclass correlation coefficient 0.5 based on prior randomized trial); a two-sided type I error rate of 0.05; and a baseline palliative care visit rate of 45% (standard deviation 10%), we expect that a sample size of 250 patients will give us 80% power to detect a meaningful 34 percentage point response in palliative care visits, considering the presence of a competing risk of 6-month mortality at 20%.

One secondary outcome will be (1) change in quality of life between 0 and 9 weeks (as measured by the Functional Assessment of Cancer Therapy – General (FACT-G) among patients who receive palliative care compared to matched controls. Multivariate linear regression analyses, adjusted for baseline scores, will be used to examine the effect of palliative care on completion of palliative care consultation for advance cancer patients. For intention-to-treat analyses, we will use the conservative method of carrying the most recent quality-of-life values forward to account for all missing data, including data that are missing owing to death.

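### The FACT-G comparison is not randomised: referral and acceptance (or receipt) filter the intervention group only, so it cannot carry an impact objective or an intention-to-treat label

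*Combined protocol and SAP*

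**What the plan says.** Pods are randomised 1:1 (Sections 5.1 and 8.2). The FACT-G groups are then formed differently in the two arms.

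- **Intervention side (8.2).** If the clinician opts out, the research team does not contact the patient. Of the remaining patients, the survey draws on this group: "Among patients in the intervention arm for whom palliative care referral is placed, who accept for a scheduler to call them to make an appointment". From these, "a trained research coordinator will approach 40" patients, described as a convenience sample.
- **Control side (8.2).** "40 randomly selected patients, matched on categories including age category and type of cancer, will be selected from the pods not receiving the intervention". No opt-out, referral or acceptance condition is stated.
- **Both sides (8.1, 8.2).** Surveys go only to patients who agree to them: "For patients that choose to enroll in the survey component".

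The outcome definition in Section 3.2, repeated in Section 9, uses receipt and not acceptance: "among patients who receive palliative care compared to matched controls". Section 8.2 itself expects the two to differ: "Patients who miss their visits with palliative care will be contacted by the coordinator".

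Section 2 gives the secondary objective as to "identify the impact of prompted palliative care referrals on quality of life". The FACT-G paragraph of Section 9 names baseline score as the only adjustment, includes no pod term, and uses an intention-to-treat label in its missing-data sentence. Section 9 also assumes that 45% of patients have a palliative care visit under usual practice.

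**The concern.** Randomising pods makes the arms comparable as assigned. It does not make a selected part of one arm comparable with an unselected part of the other. Intervention patients are surveyed only after passing clinician non-opt-out, referral placement and patient acceptance. Each of these can be related to prognosis, symptoms and willingness to engage with care. Controls who would have been opted out, or would have declined, stay in their group.

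Three further features blur what is being estimated.

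- **Population.** Accepting a call and receiving palliative care define different groups. Receipt is known only after baseline, so a literal reading removes patients who die or miss the visit from one group only.
- **Contrast.** Controls can be referred as usual, so this is neither palliative care against none nor nudge against usual care in all assigned patients.
- **Clustering.** The randomised unit is absent from the stated model.

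The outcomes at stake are the two 9-week FACT-G outcomes (3.2, 9) and the 18-week change (9). A difference, or its absence, could partly reflect who is referred, accepts or attends.

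**Working it through.** **1. The filters side by side**

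| Step | Intervention | Control |
|---|---|---|
| Clinician did not opt out | required | not applied |
| Referral placed | required | not applied |
| Patient accepts scheduling call | required | not applied |
| Selection | convenience | random, matched on categories including age and cancer type |
| Agrees to survey | required | required |
| Receives palliative care (3.2 and 9, read literally) | required | not applied |

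Only survey agreement is common to both sides.

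**2. Illustration of size**

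The plan gives no FACT-G effect size, SD or power, so there is no figure to reproduce.

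Inputs:
- n = 40 per group (Section 8.2). This is a maximum, because the number enrolled is not given.
- Two-sided 5% level. Section 9 states it for the primary endpoint; it is assumed here for FACT-G.
- q = share of controls who would have passed the filter. The plan's implied intervention-arm visit rate is 0.45 + 0.34 = 0.79. That is a design target for completed visits by 24 weeks, so it fits the receipt reading best. 0.90 is an assumption that could suit acceptance. 0.65 = 0.45 + 0.20 is an assumption that falls short of the plan's target.
- D = gap in FACT-G between patients who would and would not pass, left after matching and baseline adjustment. Assumed to be 0.2 to 0.5 SD; the documents give no source.
- Clustering ignored.

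Formulas: bias = (1 − q) × D; noncentrality = bias × √(n/2); rejection probability from the two-sided t-test with 2n − 2 degrees of freedom and no true effect.

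| q | Bias at D = 0.2 / 0.5 (SD) | Noncentrality, n = 40 | Rejection rate, n = 40 |
|---|---|---|---|
| 0.90 | 0.020 / 0.050 | 0.089 / 0.224 | 5.1% / 5.6% |
| 0.79 | 0.042 / 0.105 | 0.188 / 0.470 | 5.4% / 7.5% |
| 0.65 | 0.070 / 0.175 | 0.313 / 0.783 | 6.1% / 12.1% |

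At 30 v 30 and q = 0.79, the rates are 5.3% and 6.9%.

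**3. Bias in the other direction**

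At 40 v 40 the effect with 80% power is 0.634 SD. With q = 0.79 and the bias opposing the effect:
- 0.634 − 0.042 = 0.592 SD, power 74.4%
- 0.634 − 0.105 = 0.529 SD, power 64.7%

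**4. Exposure contrast**

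Under the receipt reading, every intervention patient and 45% of controls would have had a visit by 24 weeks: 100 − 45 = 55 points, not 100. No 9-week visit rate is given.

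**The case against.** The strongest reply is that the plan hides nothing. It says convenience sample and matched controls, and never calls the FACT-G comparison randomised. The intention-to-treat phrase sits in a sentence on missing data and can be read as keeping every surveyed patient. That is fair, and the fault is one of labelling. But the surveyed set already leaves out intervention patients who were opted out or declined, so the label does not fit even on the kind reading, and the impact objective remains.

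Several narrower objections stand in part.

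- Both groups pass through survey agreement, which may select on some of the same willingness. It does not stand in for opt-out, referral and acceptance.
- The 79% figure concerns completed visits. For a population defined by acceptance the 90% row is the closer guide, and there the error rate is nearly nominal.
- The loss of patients who die or miss visits follows only from a literal receipt definition. Carrying values forward after death and rescheduling missed visits suggest that enrolled patients may be meant to stay in. The text does not settle it.
- The 55-point contrast belongs to the receipt reading and to 24 weeks.
- The baseline data in Section 8.2 include understanding of palliative care, which bears on acceptance. It is a candidate covariate only if measured before palliative care is introduced to the patient, and the plan does not state that order.

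**Conclusion.** The concern holds. The text alone shows that the filter acts after randomisation and on one side only, and that two different analysis populations are named. Neither point depends on an assumed bias.

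The numerical effect may be modest: a false-positive rate of 5.1% to 7.5% for 79% to 90% passing, and up to 12.1% at 65%, all conditional on an assumed residual gap of 0.2 to 0.5 SD, 40 v 40 and no clustering. The direction is unknown. The main cost is to interpretation: as planned, the FACT-G results support an association, not an effect of prompted referral. The primary outcome and the outcomes measured among all patients are not touched. The change should be made, but it does not threaten the trial's main conclusion.

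**What to change.** In Section 9, with matching edits to Sections 2, 3.2 and 8.2:

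1. Drop the intention-to-treat label for FACT-G, state that this is a non-randomised matched comparison, and limit the quality-of-life objective in Section 2 to an association.
2. Name one analysis population. All enrolled survey patients, with or without a visit, is the group Section 8.2 recruits and adds no further one-sided filter. A receivers-only analysis could be a labelled sensitivity analysis.
3. Adjust for baseline FACT-G, the matching factors and a short pre-specified set already collected (ECOG status, Elixhauser index, active systemic therapy). State that this reduces but does not remove selection on willingness and opt-out.
4. Account for pod as far as the number of pods, which is not given, allows: a random intercept with small-sample degrees of freedom if estimable, otherwise a stated limitation.
5. Report palliative care visit rates in both FACT-G groups beside the result.

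Two drafting slips can be corrected at the same time; they add no weight to the point above. The regression sentence in Section 9 names consultation completion as its outcome and should name FACT-G (change to 9 weeks, 9-week score, change to 18 weeks). The baseline survey is timed before discharge in an outpatient study (8.1, 8.2); reconcile this and use the same baseline time point in both arms.

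The cost is text and analysis only: a weaker stated conclusion and a few degrees of freedom. Sampling both arms identically would remove the asymmetry, but it changes the question and the contact procedures, so it is noted as a trade-off and not requested.

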## 9. Analysis plan

We will use REDcap, a HIPAA-compliant and secure database tool, to track all components of the study. Descriptive statistics will be used to estimate the frequencies, means, and standard deviations of the study variables. Differences between study groups in baseline characteristics and clinical outcomes will be assessed with the use of two-sided Fisher's exact tests and chi-square tests for categorical variables and independent-samples Student's t-tests for continuous variables. The unit of analysis will be the patient.

The primary study endpoint is a binary patient-level variable indicating completion of a palliative care visit within 24 weeks of the clinician behavioral nudge. This analysis will be conducted as a time-to-event analysis among all eligible advanced cancer patients. Cox proportional hazard regression analyses, adjusted for baseline covariates, will be used to examine the effect of nudges on completion of palliative care consultation for advanced cancer patients. Competing risk caused by patients who die within 24 weeks will be considered as censored in the analysis. Covariates will include patient and cancer-related variables. Patients will be followed for 24 weeks or until death. Using a longitudinal multilevel mixed-effects model with clustering by discharging clinician (intraclass correlation coefficient 0.5 based on prior randomized trial); a two-sided type I error rate of 0.05; and a baseline palliative care visit rate of 45% (standard deviation 10%), we expect that a sample size of 250 patients will give us 80% power to detect a meaningful 34 percentage point response in palliative care visits, considering the presence of a competing risk of 6-month mortality at 20%.

One secondary outcome will be (1) change in quality of life between 0 and 9 weeks (as measured by the Functional Assessment of Cancer Therapy – General (FACT-G) among patients who receive palliative care compared to matched controls. Multivariate linear regression analyses, adjusted for baseline scores, will be used to examine the effect of palliative care on completion of palliative care consultation for advance cancer patients. For intention-to-treat analyses, we will use the conservative method of carrying the most recent quality-of-life values forward to account for all missing data, including data that are missing owing to death.

Other secondary outcomes will include (1) change in quality of life between 0 and 18 weeks (as measured by the Functional Assessment of Cancer Therapy – General (FACT-G) among patients who receive palliative care compared to matched controls; (2) unplanned 30-day emergency room and hospitalization rates (among all patients); (3) metrics of aggressive end-of-life care among

decedents (chemotherapy within 14 days before death, no hospice enrollment prior to death; hospice enrollment <3 days before death); (4) documented advance care planning or serious illness conversations in the outpatient medical record.

For the exploratory outcome of overall survival, survival time will be calculated from the date of enrollment to the date of death with the use of the Kaplan–Meier method. Data from patients who are alive at the last follow-up will be censored on that date. A Cox proportional-hazards model will be used to assess the effect of triggered palliative care on survival, with adjustment for baseline covariates.

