11.4 Data disclosure

11.5 Data safety and monitoring

11.6 Risk/benefit

11.6.1 Potential study risks

11.6.2 Potential study benefits

11.6.3 Risk/benefit assessment

## 1. Abstract

Patients with cancer often undergo costly therapy and acute care utilization that is discordant with their wishes, particularly at the end of life. Despite early palliative care consultations being an NCCN guideline-concordant practice in advanced cancer, palliative care referral rates for stage IV patients are low. In this project, we will evaluate a health system initiative that uses behavioral nudges to prompt palliative care referrals among outpatients with advanced cancer in terms of successful palliative care referrals and downstream quality of life outcomes. In partnership with the health system, this will be conducted as a 2-arm pragmatic cluster randomized trial.

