### *3.3 Exploratory outcomes*

- Unplanned 30-day emergency room and hospitalization rates (among all patients)
- Metrics of aggressive end-of-life care (systemic therapy within 14 days before death, no hospice enrollment prior to death; hospice enrollment <3 days before death) among decedents
- Documented advance care planning or serious illness conversations in the outpatient medical record
- Hospice referral and enrollment among all patients
- Overall survival, defined as date from enrollment to death

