## 5. Study design

### 5.1 Design

This is a 2-arm pragmatic randomized trial among approximately 250 outpatients with advanced cancer to assess response to behavioral nudges to refer to palliative care. The setting will be outpatient oncology at the Ann B. Barshinger Cancer Institute at Lancaster General Health. Eligible clinicians will be randomized in clusters by overlapping clinical team (pod) to receive default EPIC-based prompts for palliative care referral among advanced cancer patients (Arm 1) vs no intervention/usual practice (Arm 2). These nudges have been shown to positively influence clinician behavior and are often used to drive value-based oncology care; however, they have never been studied in the context of palliative care referral. The primary outcome is completion of a palliative care referral within 12 weeks of enrollment.

Following the intervention, brief REDCap questionnaires will be sent to all clinicians who participated in the trial to explore perceptions of the study intervention. This survey should take no longer than five minutes for clinicians to complete and will assess their feedback on the overall intervention in addition to specific components including automated identification of patients, receiving text and email notifications, and identifying the appropriate patients. The survey will also collect basic demographic information (age, gender, practice site, and comfort with SICs) (**Appendix 3**).

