### *8.2 Procedures*

Baseline data on oncologists and their patients at Lancaster General Health will be obtained from Penn Data Store and Clarity (Epic's data reporting database). Physician data includes demographic information (e.g. sex, type of medical degree, etc.) and may be also obtained from publicly available databases or websites online. Baseline data collected on patients will include age, gender, zip code of residence, type of cancer, Elixhauser comorbidity index, ECOG performance status, whether the patient is on active systemic therapy, and understanding of palliative care. This will be collected via the electronic health record and an in-person enrollment questionnaire (**Appendix D**) upon enrollment into the trial. Those who elect not to participate, but consent to limited data collection, will be asked to fill out a similar questionnaire including reason(s) for not wanting to participate in a de-identified manner (**Appendix E**).

Prior to the trial, staff will randomize each clinician pod in a 1:1 fashion to either intervention or usual care. The Principal Investigator ([name]) will be blinded to arm assignment. In both intervention and control arms, research coordinator staff will identify patients with advanced cancer who are actively cared for within the Ann B. Barshinger Cancer Institute system. They will then regularly review the electronic health record for eligible clinicians to identify patients with an upcoming repeat patient visit who are eligible for palliative care. Patients who are eligible will have a solid malignancy and at least one of the following five conditions: (1) Documented advanced (stage IV) solid malignancy; (2) Known central nervous system metastasis, (3) Eastern Cooperative Oncology Group performance status  $> 2$ , Karnofsky Performance Status  $< 50$ , (4) uncontrolled symptoms such as pain, escalating opioids, nausea/vomiting, distress, dyspnea, delirium, or (5) hospitalization relevant to cancer or treatment.

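### Pods are randomised, but the primary Cox model has no pod term, so the two-sided 0.05 is not protected; the excess depends on a pod count and pod ICC that the plan does not state

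*Combined protocol and SAP*

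**What the plan says.** The Abstract says that "this will be conducted as a 2-arm pragmatic cluster randomized trial". Section 5.1 adds "Eligible clinicians will be randomized in clusters by overlapping clinical team (pod", and section 8.2 says that "staff will randomize each clinician pod in a 1:1 fashion to either intervention or usual care". In the intervention arm, "the care team pod will receive an EPIC in-basket message" (section 8.2). The pod is therefore both the randomised and the treated unit.

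Section 9 then states "The unit of analysis will be the patient". For the primary endpoint it specifies: "Cox proportional hazard regression analyses, adjusted for baseline covariates, will be used to examine the effect of nudges on completion of palliative care consultation". On the adjustment set it says "Covariates will include patient and cancer-related variables". No pod term, frailty, cluster-robust variance or pod-level test is named.

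Clustering appears once in section 9, in the sentence that justifies 250 patients. That sentence refers to a longitudinal mixed-effects model clustered by discharging clinician, with an ICC of 0.5. The documents do not give the number of pods, their composition or a pod-level ICC.

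The other between-arm tests in section 9 (Fisher, chi-square and t-tests for clinical outcomes, and a Cox model for survival) are also unclustered. One outcome they would cover, "Unplanned 30-day emergency room and hospitalization rates (among all patients", is exploratory in section 3.3 but listed among the secondary outcomes in section 9.

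**The concern.** Arm is constant within a pod, so any difference between pods in referral habit or case mix that the covariates do not explain falls directly on the treatment contrast. A Cox model that treats patients as independent leaves this variance out of the standard error, and a chance difference between pods can then pass for a nudge effect. With many pods or a very small pod ICC the harm is slight. With few pods or a larger ICC, a significant primary result would be weak evidence. The plan omits the two quantities needed to tell which case applies.

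**Working it through.** **Inputs from section 9.** N = 250; two-sided alpha 0.05; control visit rate 45% with SD 10%; effect 34 points (45% to 79%); 20% mortality at 6 months; clinician ICC 0.5; 24 weeks of follow-up. **Assumed, because not stated:** 6, 10, 14, 20 or 36 equal pods, and the pod-level ICC.

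**1. The plan's 80% power.** It cannot be reproduced without the number of clusters. Ignoring clustering, 45% versus 79% needs 31 patients per arm, and 125 per arm gives over 99.9% power. The stated 80% must therefore already contain a large allowance for clustering. With design effect DE = 1 + (m − 1) × ICC, m = 250/clusters and ICC 0.5, 80% needs about 36 clusters: m = 6.9, DE = 3.97, power 0.81. With 12 clusters, power is 0.38.

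**2. Candidate ICCs on the proportion scale.**
- If the SD of 10% is between pods: 0.10² / (0.45 × 0.55) = 0.0404.
- An ICC of 0.5 implies a between-cluster SD of √(0.5 × 0.45 × 0.55) = 0.352, or 35 points. This conflicts with 10% if that SD is between clusters.
- If 0.5 is on a logistic latent scale, it corresponds to about 0.36 on the proportion scale.

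**3. Type I error of the unclustered test.** The approximation is 2 × (1 − Φ(1.96/√DE)). Example with 6 pods and ICC 0.0404: m = 41.7, DE = 1 + 40.7 × 0.0404 = 2.64, 1.96/√2.64 = 1.21, giving 22.8%. The check is a null simulation with beta-distributed pod rates (mean 45%), exponential visit times, 20% of patients dying and censored, and a Cox Wald test with arm only (20,000 replicates per cell). Simulated %, with the formula in brackets:

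| Pod ICC | 6 pods | 10 | 14 | 20 | 36 |
|---|---|---|---|---|---|
| 0.01 | 9.4 (9.8) | 7.6 (7.8) | 6.8 (7.0) | 6.2 (6.3) | 5.3 (5.7) |
| 0.0404 | 22.3 (22.8) | 15.5 (16.3) | 12.7 (13.1) | 10.0 (10.5) | 7.9 (7.8) |
| 0.1 | 37.5 | 28.4 | 22.7 | 17.2 | 11.8 |
| 0.5 | 68.4 (67.1) | 59.8 (58.7) | 53.5 (52.3) | 45.5 (45.1) | 33.1 (32.5) |

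At ICC 0 the simulated size is 4.2% to 5.1%. At ICC 0.36 it is about 62 / 53 / 46 / 39 / 27%. A second simulation, with log-normal pod effects on the hazard, gives 13.8% for 12 pods and 9.8% for 20 at ICC about 0.04, in line with the table.

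**4. Understatement of the standard error (√DE, 6 to 36 pods).** The factor is 1.2 to 1.03 at ICC 0.01, 1.6 to 1.1 at 0.04, and 4.6 to 2.0 at 0.5.

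**5. If the analysis were clustered by clinician instead.** This was simulated as a Cox model with clinician-robust variance and t on clinicians − 2 df, for 6 to 20 pods of 2 or 3 clinicians and 36 pods of 2 (4,000 replicates per cell).

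| Share of clinician variance lying between pods | Size at clinician ICC 0.5 | Size at clinician ICC 0.04 |
|---|---|---|
| None | 4–6% | 5–7% |
| A quarter | 6–11% | 6–9% |
| Half | 10–19% | 5–11% |
| All | 15–34% | 7–15% |

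**The case against.** The strongest reply is that section 9 does mention clustering, in the same paragraph as the primary endpoint, and that the mixed-effects sentence may be meant as the analysis. The defect would then be an unreconciled model and cluster level. This reading does not rescue the plan. The sentence supports a power claim, names a model other than Cox, and clusters by clinician. Clinicians sit within pods, so a clinician term alone leaves between-pod variance uncovered (step 5). The excess would go if pods were single clinicians, but section 5.1 describes pods as overlapping teams. Step 5 also grants a t reference that the plan does not state. With a normal reference, a balanced random-intercept model has size 2 × P(t on k − 2 df > 1.96), about 12 / 9 / 7 / 6% for 6 / 10 / 20 / 36 clusters.

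Three further points stand as qualifications:
- The simulated Cox model has arm only, whereas the plan adjusts for covariates. The relevant ICC is the residual one, which is smaller if case mix explains part of the pod differences. Differences in practice style would remain.
- Every size above depends on assumed pod counts and ICCs. The cells at ICC 0.5 borrow a clinician figure and should be read as an upper scenario.
- The outcomes other than the primary are exploratory or secondary, so for them the point is one of consistency.

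**Conclusion.** The concern holds, and the plan should be corrected before analysis. No reading of section 9 puts the randomised pod into the primary test, so the declared two-sided 0.05 is assured only if residual pod-level variance is zero. The excess is of unknown size. It is negligible with 36 pods at ICC 0.01 (about 5%). It is material with 6 to 14 pods at ICC 0.04 (22% to 13%). It is severe if an ICC near the plan's own 0.5 applied to pods. The figures assume equal pod sizes, 250 patients and ICCs on the proportion scale.

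**What to change.** In section 9:
- State the number and composition of pods, and make the pod, not the discharging clinician, the cluster.
- Name one primary analysis that accounts for pod and is valid for the number of pods available.
- Restate power from the pod count and a pod-level ICC, and give the scale of that ICC.
- For consistency, use the pod as the cluster in the other randomised between-arm comparisons.

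**Choice of method.** With fewer than about 20 pods, use a pod-level test with a t reference on pods − 2 df. Pod means of martingale residuals from a covariate-only Cox model keep the time-to-event handling and the stated censoring at death. In null simulations with 6 to 36 pods, equal and unequal in size, and ICC 0.01 to 0.5, this test had size 4.2% to 6.3%. It gives a p-value but no hazard ratio, so the plan must also say how the effect and its interval will be estimated. Pod visit proportions hold the error rate too (4.2% to 6.5%), but they count patients who die unvisited as non-visits; if they are used, say that the estimand changes. A Cox model with pod-robust variance and t on pods − 2 df had size 8.2% to 12.8% with 6 pods, 5.2% to 7.3% with 20 and 4.6% to 6.0% with 36. It is an adequate alternative from about 20 pods, though that threshold is not sharp.

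**Cost.** SAP wording, a little code and a recomputed power statement, with wider intervals and possibly lower power. For 45% versus 79%, the power of a t-test on pod proportions (noncentral t, pod-mean variance p(1 − p)(ICC + (1 − ICC)/m)) is:

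| Pod ICC | 6 pods | 10 | 14 | 20 | 36 |
|---|---|---|---|---|---|
| 0.01 | 80–95% | 94–100% | 97–100% | 98–100% | 99–100% |
| 0.04 | 55–77% | 80–96% | 89–99% | 94–100% | 97–100% |
| 0.1 | 33–51% | 57–80% | 71–91% | 82–97% | 93–100% |
| 0.5 | 12–17% | 19–30% | 27–43% | 37–58% | 59–82% |

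The lower ends assume that 20% mortality removes a fifth of the rates and of the effect. The stated 80% survives a small pod ICC but may be out of reach with few pods and a larger one.
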